OFFICIAL TITLE:

"Intraoperative Continuous Noninvasive Hemoglobin Monitoring in Patients Undergoing Thoracic Surgery"

NCT NUMBER: still not available

DOCUMENT DATE:

July 13, 2024

Intraoperative continuous noninvasive hemoglobin monitoring in patients undergoing thoracic surgery.

Background: hemoglobin levels similar to how a pulse oximeter provides continuous oxygen saturation. The spot check hemoglobin monitor works by the same principle as the continuous monitor but is a point-of-care device that calculates the serum hemoglobin level within 1 min of placement of the probe. The accuracy and reliability of both these monitors vary and the clinical applicability in trauma remains to be defined. Accuracy of continuous non-invasive hemoglobin monitoring.

Methods: This observational study evaluated the correlation between noninvasive hemoglobin monitoring (SpHb) and invasive hemoglobin measurements (InvHb) in guiding blood transfusions during thoracic surgery. A total of 80 patients aged 18 years or older, all scheduled for thoracic procedures between July 2024 and July 2025, were enrolled. Continuous SpHb monitoring was performed throughout the surgeries, with simultaneous InvHb samples collected to validate the readings. The primary outcome will be the degree of correlation between SpHb and InvHb values.

Introduction:

Technology has always been an essential component of patient care. As technology has advanced over the years, the way we have practiced medicine has evolved as well. Perhaps no field in medicine has been affected by technology as much as surgery. From operations being performed without any pain control to robotic surgery, technology has completely revamped our practice of surgical care and the field of trauma surgery and critical care remains no exception. One of the major influences of technology on patient care has been the shift in paradigm away from highly invasive diagnostic and therapeutic procedures to non-invasive procedures. This has resulted in reduced time for diagnosis, critical decisions making, and treatment as well as improved patient satisfaction. Hemoglobin measurement is one of the most frequently performed laboratory tests after injury [1]. Non-invasive hemoglobin monitoring is a more recent introduction to the growing list of point-of-care testing capabilities that allows for the ability to monitor hemoglobin concentration in a continuous, accurate, and non-invasive fashion [2]. It is still growing in popularity and it is our impression that many trauma and critical care providers do not know about its utility nor the basic principles behind the mechanism of function. In this review, we will briefly discuss the basic principles of how non-invasive hemoglobin monitoring technology works, the different factors that affect its accuracy, and demonstrate how this technology may translate into added benefits to patient care.

Invasive measurement, although accurate is time-consuming, costly, painful for the patient, and may have potential risk for exposure to biohazards. It can significantly delay patient care because of the time required for the phlebotomy, transport of the sample to the laboratory, time required for analysis and validation, and the reporting of results back to physician. Hemoglobin (Hgb) measurement is one of the most frequently ordered laboratory tests in the trauma settings; it can help guide therapeutic plan of management [1]. In trauma patients, these decisions range from blood transfusions to operative intervention. There has been a significant paradigm shift towards non-operative management in trauma patients and the rate of operative intervention in blunt abdominal and pelvic trauma has significantly declined. The majority of these patients are managed non-operatively and undergo surgical intervention only for ongoing bleeding or hemodynamic instability [3,4]. This approach however requires close monitoring in the Intensive Care Unit (ICU) and repeated phlebotomy for hemoglobin measurement to assess for ongoing hemorrhage [5]. The use of continuous or spot-check non-invasive hemoglobin monitoring provides the ability to monitor these patients in real time and react to changes in hemoglobin levels. A Cochrane review from ten trials reported outcomes on 1780 patients and found that a restrictive transfusion strategy is associated with 20% lower mortality, reduced hospital and ICU length of stay [6]. On the other hand, post operative anemia is also associated with increased post operative morbidity and mortality [7]. Accurate continuous measures of hemoglobin can help avoid the extremes of over or under transfusion. This is another avenue where a quick non-invasive measurement of hemoglobin can help in the implementation of restrictive transfusion strategy.

3. Basics of function

There is some variation in the basic principles that govern the functioning of most commercially available non-invasive devices. Most non-invasive hemoglobin measurement devices rely on spectrophotometry. Light is transmitted through or reflected from tissues and blood differentially depending on their biochemical variables. This difference in the degree of reflection allows for calculation of the hemoglobin and hematocrit using a mathematical model [8]. Other devices rely on photoplethysmography, which is the study of volume changes in the body. They detect the relative magnitude of the photoplethysmographic signal at different times of the cardiac cycle using different wavelengths of light. Separate photodetectors detect this signal and utilize it to determine the hemoglobin content and hematocrit of blood [9,10].

4. Non-invasive hemoglobin monitors

Masimo Corporation (Irvine Ca.) has developed a Pulse COoximeter capable of measuring hemoglobin concentration using a noninvasive, multi-wavelength sensor for spot check and continuous measurement: the Radical 7 (Rad7) [11]. The technology emits multiple wavelengths of light and then calculates the hemoglobin concentration based on the adsorption of light in the blood [12]. The device uses a finger tip probe similar to a standard pulse oximeter sensor and determines the hemoglobin noninvasively. There are two types of hemoglobin measuring devices; continuous hemoglobin monitor and spot check hemoglobin monitor. The continuous non-invasive hemoglobin monitor, as the name suggests, monitors serum hemoglobin continuously and provides real time

References

[1] B. Joseph, V. Pandit, H. Aziz, et al., Transforming hemoglobin measurement in trauma patients: noninvasive spot check hemoglobin, *J. Am. Coll. Surg.* 220 (1) (2015) 93e98.

[2] B. Joseph, P. Hadjizacharia, H. Aziz, et al., Continuous noninvasive hemoglobin monitor from pulse ox: ready for prime time? *World J. Surg.* 37 (3) (2013) 525e529.

[3] K.J. Brasel, C.M. DeLisle, C.J. Olson, D.C. Borgstrom, Splenic injury: trends in evaluation and management, *J. Trauma Acute Care Surg.* 44 (2) (1998) 283e286.

[4] H.L. Pachter, A.A. Guth, S.R. Hofstetter, F.C. Spencer, Changing patterns in the management of splenic trauma: the impact of nonoperative management, *Ann. Surg.* 227 (5) (1998) 708e719.

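### The aim speaks of guiding transfusion, but the only stated outcome, correlation of SpHb with InvHb, cannot show whether the two methods agree at a transfusion threshold

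*Protocol*

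**What the plan says.** The Methods paragraph of the protocol describes an observational study that "evaluated the correlation between noninvasive hemoglobin monitoring (SpHb) and invasive hemoglobin measurements (InvHb) in guiding blood transfusions during thoracic surgery". SpHb is recorded continuously through surgery, "with simultaneous InvHb samples collected to validate the readings". The paragraph then fixes one outcome: "The primary outcome will be the degree of correlation between SpHb and InvHb values". The sample is given as "A total of 80 patients aged 18 years or older".

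The document names no other outcome and no hemoglobin threshold. It does not give the number of pairs per patient, and it does not say that SpHb readings direct transfusion in this study.

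The Introduction, which is general background written largely about trauma care, gives the reason for interest in the device: "Accurate continuous measures of hemoglobin can help avoid the extremes of over or under transfusion", and "a quick non-invasive measurement of hemoglobin can help in the implementation of restrictive transfusion strategy".

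**The concern.** Using a hemoglobin value to guide transfusion means acting on where it lies relative to a cut-off. Correlation measures how closely two sets of values follow a straight line. It is unchanged if a constant is added to every SpHb reading or if SpHb is multiplied by any positive factor. A device that reads consistently high and one that reads consistently low can therefore have the same correlation with InvHb while making opposite errors at the cut-off: the first misses low values, the second raises false low alarms. The Introduction names over- and under-transfusion as the two errors to avoid, and a correlation separates neither.

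The risk lies in the conclusion. Under an aim worded this way, a high correlation could be reported as support for using SpHb in transfusion decisions, although the same figure is compatible with a device that misses most low values.

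**Working it through.** The protocol gives no figure to reproduce here: no target correlation, bias, error SD, threshold or count of low values. The mismatch follows from the definition of correlation. The numbers below only show how large it can be, and **every input is an assumption, none from the protocol**.

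**Model.** X = InvHb, centred at its mean, normal with SD 1.5 g/dL. Y = SpHb = X + b + e, with constant bias b and independent error e, SD s. Threshold T = -c × 1.5, that is, c SDs below the InvHb mean. Let J = P(X < T and Y < T), from the bivariate normal distribution. Then:

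- r = 1.5 / √(1.5² + s²), which does not contain b
- share of low values flagged (sensitivity) = J / P(X < T)
- share of flags that are correct (PPV) = J / P(Y < T)
- missed-low = P(X < T) − J; false-low = P(Y < T) − J; total discordance is their sum

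**Base case, s = 1.0, c = 1.5.** r = 1.5 / √3.25 = 0.832 and P(X < T) = 0.0668.

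| Bias (g/dL) | r | P(Y < T) | J | Low values flagged | Flags correct | Missed-low, all pairs | False-low, all pairs | Total discordance |
|---|---|---|---|---|---|---|---|---|
| −1 | 0.83 | 0.2440 | 0.0621 | 93% | 25% | 0.5% | 18.2% | 19% |
| 0 | 0.83 | 0.1060 | 0.0475 | 71% | 45% | 1.9% | 5.9% | 8% |
| +1 | 0.83 | 0.0357 | 0.0249 | 37% | 70% | 4.2% | 1.1% | 5% |

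Total discordance falls from 19% to 5% while missed low values rise from 0.5% to 4.2% of all pairs. A single discordance rate would therefore also mislead, and the two directions need separate reporting.

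**Range at zero bias.**

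| s (g/dL) | c | r | Low values flagged | Flags correct |
|---|---|---|---|---|
| 0.7 | 1.5 | 0.91 | 76% | 59% |
| 1.3 | 1.5 | 0.76 | 67% | 35% |
| 1.0 | 1 | 0.83 | 74% | 58% |
| 1.0 | 2 | 0.83 | 69% | 33% |

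**Second set of assumptions.** InvHb mean 11 g/dL, both methods with SD 1.5 g/dL, r = 0.90, and a cut-off of 10 g/dL taken purely as an arithmetic example. The share of InvHb values below the cut-off that SpHb places at or above it is 23% with no bias, 65% at +1 g/dL and 91% at +2 g/dL, all at the same r. With 80 patients and one pair each (assumed), the 95% Fisher interval for r = 0.90 is 0.85 to 0.94. A precise r therefore does not narrow the range of misclassification.

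**How well a threshold analysis could be estimated.** This depends on the number of low pairs, which is unknown. Exact (Clopper-Pearson) 95% intervals for sensitivity, before any widening for repeated pairs within patients:

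- 4 of 5 (80%): 28% to 99%
- 14 of 20 (70%): 46% to 88%
- 36 of 50 (72%): 58% to 84%

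With one pair per patient and the base-case threshold, 80 × 0.0668 gives about 5 low pairs.

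**The case against.** The strongest reply is that this is a wording point. What the study says it evaluates is the correlation, and that matches the primary outcome; the transfusion phrase can be read as clinical context. No success criterion says a high correlation would endorse SpHb-guided transfusion, and agreement or threshold analyses may sit in an SAP that is not shown. This has some force: the correlation result is valid for what it is, and deleting a few words would cure the mismatch. But the aim and the primary outcome are both set in the protocol. An SAP can add analyses around them, but it leaves the two sentences as they stand.

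A second reply is that the protocol names no coefficient, and that a concordance correlation would respond to bias. It would: in the base case it is 2 × 1.5² / (1.5² + 3.25 + b²), which is 0.82 at zero bias and 0.69 at a bias of 1 g/dL. Because b enters squared, it is 0.69 at both −1 and +1 g/dL, where 93% and 37% of low values are flagged. The direction of error is still lost.

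Third, the inputs are invented and the proposed analysis may be imprecise. Both are true. The inputs affect only the size of the illustration. The imprecision is a real limit, and with about 5 low pairs a sensitivity estimate would be close to uninformative. That argues for stating beforehand when the threshold result will be interpreted, or for narrowing the aim. The Introduction is also only background on trauma care, so it supports the point without establishing it.

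**Conclusion.** The concern holds. As written, the plan cannot answer the transfusion part of its own aim, because no value of the stated outcome fixes how often, or in which direction, the two methods disagree at a threshold. That conclusion needs no assumed numbers. Its practical size does: under the base-case assumptions, one correlation of 0.83 covers sensitivities for low values from 37% to 93% over a bias range of ±1 g/dL. The actual bias, error spread, hemoglobin distribution and threshold for this trial are not in the document. The correlation result itself is unaffected; what lacks support is the transfusion claim attached to it. The change should be made, but the flaw does not invalidate the study.

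**What to change.** Keep the primary outcome and add one prespecified secondary outcome from the paired samples already planned:

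- Classify each SpHb and InvHb value as below or not below the transfusion threshold(s) the site already uses. The protocol states none, so the sponsor would need to record them; no threshold is proposed here.
- Report sensitivity, specificity, and the missed-low and false-low proportions separately, with confidence intervals that allow for clustering by patient. Give bias and limits of agreement alongside.
- State in advance the minimum number of low pairs, or the interval width, needed to interpret the result. If it is not reached, limit the conclusion to measurement agreement and drop the transfusion wording.

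If no decision-level outcome is wanted, remove the transfusion wording from the aim now.

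The first option costs one 2x2 table per threshold and a sentence in the protocol, with no extra sampling. Its downside is that low-range estimates may be imprecise and the claim may have to be narrowed. The wording-only option costs nothing.

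### Does leaving the timing and number of the invasive hemoglobin draws unstated undermine the primary correlation?

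*Protocol*

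**What the plan says.** The Methods paragraph is the only design text in the protocol. It enrols the cohort ("A total of 80 patients aged 18 years or older, all scheduled for thoracic procedures between July 2024 and July 2025, were enrolled"), describes the measurements ("Continuous SpHb monitoring was performed throughout the surgeries, with simultaneous InvHb samples collected to validate the readings") and names the endpoint: "The primary outcome will be the degree of correlation between SpHb and InvHb values". It places the comparison in a clinical use, "in guiding blood transfusions during thoracic surgery". The word for simultaneity fixes how a device reading is matched to a blood sample. The paragraph gives no time points, number of draws per patient or trigger for a draw, and no explicit statement that every patient contributes.

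The Introduction and the sections on how the devices work are general background and add no schedule. The Introduction does give the transfusion rationale ("Accurate continuous measures of hemoglobin can help avoid the extremes of over or under transfusion") and describes the burden of blood sampling: "Invasive measurement, although accurate is time-consuming, costly, painful for the patient".

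**The concern.** A correlation is not a property of the device alone. For a given device error, r is larger when the sampled hemoglobin values are more spread out, and the time of the draws affects that spread. One pair per patient before incision and pairs taken before and after blood loss are both compatible with the text, yet they can target different correlations.

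The stated use adds to the worry. Transfusion decisions arise at low hemoglobin, and no sentence guarantees a pair after blood loss. If draws followed clinical need alone, some patients might give no pair, and 80 patients would not mean 80 pairs. Draw timing is study conduct, so an analysis plan could not recover pairs that were never taken. At stake would be a primary result that depends on an unwritten choice, with few data in the range that matters.

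**Working it through.** **The plan's own figure.** The protocol gives 80 patients with no derivation and no expected correlation, so there is no calculation to reproduce. Every input below other than 80 is an assumption.

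**Inputs (assumed).** Pre-incision hemoglobin SD, sB: 1.0 or 1.5 g/dL. Device error SD, se: 0.7, 1.0 or 1.3 g/dL. Intraoperative fall, mean mD / SD sD: 0.5/0.3, 1.0/0.7 or 2.0/1.2 g/dL. This makes 2 × 3 × 3 = 18 combinations.

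**Formula.** r = √(V/(V + se²)), where V is the variance of the sampled hemoglobin:
- pre-incision pairs: V = sB²
- end-of-surgery pairs: V = sB² + sD²
- both pooled: V = sB² + sD²/2 + mD²/4

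The last two assume that the fall is independent of baseline. All three assume a constant device error.

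**Worked example (sB = 1.0, se = 1.0, largest fall).**
- Pre-incision: √(1/2) = 0.71.
- End: V = 1 + 1.44 = 2.44, r = √(2.44/3.44) = 0.84.
- Pooled: V = 1 + 0.72 + 1 = 2.72, r = √(2.72/3.72) = 0.86.

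**Whole grid.** Rise in r over pre-incision pairs (end or pooled):

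| Assumed fall (mean/SD) | Rise in r |
|---|---|
| 0.5/0.3 | 0.003–0.019 |
| 1.0/0.7 | 0.015–0.075 |
| 2.0/1.2 | 0.033–0.176 |

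**Against sampling error.** The 95% half-width is about 1.96(1 − r²)/√(n − 3). With n = 80 and r = 0.707 it is 1.96 × 0.5/√77 = 0.112. Taking the larger of the two shifts in each cell and the half-width at that cell's pre-incision r:
- All 12 cells with the small or middle fall lie inside the half-width.
- With the largest fall and sB = 1.5, the larger shifts are 0.037, 0.062 and 0.082 against half-widths of 0.040, 0.069 and 0.096: inside.
- With the largest fall and sB = 1.0, they are 0.101, 0.148 and 0.176 against 0.073, 0.112 and 0.140: outside.

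So 15 of 18 lie inside. The worked example above is one of the three outside.

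**Relaxing independence.** If fall and baseline are correlated at 0.5 (assumed; for instance, loss roughly proportional to the starting level), the end variance becomes sB² + sD² − 2 × 0.5 × sB × sD. In the worked example this is 2.44 − 1.2 = 1.24, so r = √(1.24/2.24) = 0.744 and the gain drops from 0.135 to 0.037. The pooled gain drops from 0.148 to 0.117. Over the grid, end minus pre-incision is negative in 15 of 18 cells.

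**Low values.** Expected pairs at least 3 g/dL below the pre-incision mean (an arbitrary mark), out of 80:
- Pre-incision draws, 80 × Φ(−3/sB): 0.1 (sB = 1.0) and 1.8 (sB = 1.5).
- End draws, 80 × Φ((mD − 3)/√(sB² + sD²)): 0.7–4.1, 4.1–9.1 and 20.9–24.1 for the three falls.

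Pre-incision draws alone would therefore say little at low hemoglobin.

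**The case for a change.** The strongest case for acting is that the gap is real and belongs to the protocol. Simultaneity fixes the matching and nothing else, and nothing elsewhere in the document supplies a schedule. Being inside the half-width does not make a shift vanish: it is systematic and would not average out. Larger effects can also be constructed. With error SD 1.0, r runs from 0.63 to 0.93 as the sampled SD goes from 0.8 to 2.5 g/dL. With true hemoglobin of mean 12 and SD 1.5, drawing blood only when the device reads below 10 lowers r from 0.83 to 0.55 and gives a mean bias of −0.9 g/dL.

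The dependence of r on sampling stands, and so does the absence of a schedule. The step to a defect does not. Sampling wholly or mostly before incision is the least natural reading of a study titled intraoperative, with monitoring through the operation and a use during surgery. Device-triggered sampling has no basis in the text. Sampling is described without restriction straight after the 80 patients are named, so restriction to a subset is not suggested either. The number of draws mainly affects precision and clustering, and the handling of repeated pairs is ordinary analysis-plan content. Pairing the blood samples that care already produces is a legitimate observational design.

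**Conclusion.** No change to the plan is called for. The Methods paragraph is short on detail but states nothing false and contradicts nothing. Simultaneous pairs taken during surgery in the enrolled patients give a sound correlation, and investigators can fill in the draw points from their sampling routine. Reporting the SD and range of the invasive values beside r would let a reader judge the effect of spread, and that is normal reporting practice.

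On size, clearly different primary results are not shown. The shift stays within the 95% half-width at 80 pairs in 15 of 18 assumed combinations. It exceeds it only when a mean fall of 2.0 g/dL meets a baseline SD of 1.0 g/dL. A rise with end-of-surgery draws depends on the fall being unrelated to baseline; at a correlation of 0.5 it reverses in 15 of 18. These figures rest entirely on assumed SDs, falls and a constant device error.

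A mandated pair before incision and at the end in every patient could need 2 × 80 = 160 samples, some possibly beyond routine care, with the burden the Introduction itself describes. That is a poor exchange for an effect this uncertain. The conclusion would differ if the investigators in fact drew blood only before incision or only on low device readings, but nothing in the protocol indicates either.

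### Does the primary correlation pool repeated SpHb-InvHb pairs from the same patient as if they were independent?

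*Protocol*

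**What the plan says.** The only design content is the Methods paragraph at the start of the Protocol. It sets out four things:

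- Sample size: "A total of 80 patients aged 18 years or older".
- Aim: "This observational study evaluated the correlation between noninvasive hemoglobin monitoring (SpHb) and invasive hemoglobin measurements (InvHb) in guiding blood transfusions during thoracic surgery".
- Data collection: "Continuous SpHb monitoring was performed throughout the surgeries, with simultaneous InvHb samples collected to validate the readings".
- Primary outcome: "The primary outcome will be the degree of correlation between SpHb and InvHb values".

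The paragraph does not say how many invasive samples each patient gives or when they are drawn. It names no correlation coefficient, no unit of analysis and no confidence interval. The protocol has no statistical methods section, and the SAP was not available for this review.

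**The concern.** A monitor that runs through a whole operation invites comparison at several times, and the protocol speaks of samples and values in the plural. Read that way, one patient supplies several SpHb-InvHb pairs. These pairs share the patient's own hemoglobin level and any offset of the device in that patient, so they are not independent.

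Putting all such pairs into one ordinary correlation would have three consequences. The coefficient would blend two questions: whether patients with higher InvHb also show higher SpHb, and whether SpHb follows InvHb as it changes within a patient. A confidence interval based on the number of pairs would claim more precision than 80 patients can give. Patients sampled more often would also weigh more. Because the study is about guiding transfusion, a coefficient that looked strong mainly because patients differ from one another could mislead.

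**Working it through.** **1. What the document supplies.** The only usable number is 80 patients. Pairs per patient (m), hemoglobin standard deviations, device error, intraclass correlation (ICC), target correlation and confidence level are all unstated. The protocol gives no derivation of the 80, so there is no planned figure to reproduce. Every other input below is an assumption.

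**2. Does pooling mix two associations?** If both methods have the same ICC, the pooled coefficient is

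r_pooled = ICC × r_between + (1 − ICC) × r_within.

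With r_between = 0.8 and r_within = 0.4:

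- ICC 0.3: 0.3 × 0.8 + 0.7 × 0.4 = 0.52
- ICC 0.9: 0.9 × 0.8 + 0.1 × 0.4 = 0.76

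A second illustration assumes true hemoglobin SDs of 1.3 g/dL between and 0.7 g/dL within patients, and a device error SD of 1.0 g/dL. True variance is 1.69 + 0.49 = 2.18, so pooled r = √(2.18/3.18) = 0.83. If 30%, 50% or 70% of the error variance is shared within a patient, within-patient r is √(0.49/1.19) = 0.64, √(0.49/0.99) = 0.70 or √(0.49/0.79) = 0.79. So mixing does occur when repeated pairs are pooled.

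**3. How much would a naive interval shrink?** The Fisher-z 95% interval is tanh(atanh(r) ± 1.96/√(n − 3)). At r = 0.70:

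| Pairs counted as independent | 95% interval |
|---|---|
| 80 (m = 1) | 0.568 to 0.797 |
| 160 (m = 2) | 0.611 to 0.771 |
| 240 (m = 3) | 0.629 to 0.759 |
| 400 (m = 5) | 0.646 to 0.747 |

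**4. Is the shrinkage unjustified?** Two-level bivariate normal data were simulated for 80 patients, with the same m for every patient and 2,000 runs per setting. The between- and within-patient correlations were both 0.7, or 0.8 and 0.4, or 0.4 and 0.8.

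| m | ICC | Coverage of naive 95% interval | True SE / naive SE |
|---|---|---|---|
| 1 | 0 to 0.9 | about 95% | about 1.0 |
| 2, 3 or 5 | 0 | about 95% | about 1.0 |
| 2 | 0.5 to 0.9 | 84% to 92% | 1.1 to 1.4 |
| 3 | 0.5 to 0.9 | 77% to 91% | 1.1 to 1.6 |
| 5 | 0.5 to 0.9 | 65% to 87% | 1.3 to 2.1 |

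Coverage falls short only when three conditions hold together: more than one pair per patient, correlation within patients, and an analysis that ignores it. Because m was equal for all patients, the simulation does not address extra weight for patients sampled more often.

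**5. Does the protocol meet these conditions?**

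- *More than one pair per patient.* The wording "simultaneous InvHb samples collected" refers to a study of 80 patients, and one sample from each already makes 80 samples. Continuous SpHb recording does not by itself require serial InvHb draws. Several pairs are plausible but not stated.
- *Correlation within patients.* This is likely if pairs are repeated, but it has no meaning with one pair each.
- *An analysis that ignores it.* The outcome is given only as "degree of correlation between SpHb and InvHb values". A repeated-measures coefficient, or separate between- and within-patient coefficients, would satisfy that sentence as well as a pooled one. The word for the measurements does not make the pair the unit of analysis, since one pair per patient also gives 80 values of each kind. No interval is mentioned, so none can be called too narrow.

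The first condition is left open, the second depends on it, and the third is not found in the text.

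**The case for a change.** The strongest reply is that the protocol, and not the SAP, defines the primary outcome. As worded, that outcome could mean association between patients, tracking within a patient, or a mixture. The Introduction promotes the technology for following hemoglobin in real time, which is a within-patient question. Nothing limits a patient to one pair, repeated sampling is the natural way to validate a continuous monitor, and a sentence on the unit of inference would cost almost nothing.

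Much of this is fair. The mechanism is real, several pairs per patient are plausible, and the brevity of the protocol leaves the reader to guess. If repeated pairs are taken, the analysis must account for them. It is also true that one pair per patient could not show tracking of change, but the primary outcome sentence does not claim to measure tracking.

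The reply still shows only that the text permits a poor analysis, not that it prescribes one. The type of coefficient, the treatment of repeated measurements and the interval method are ordinary SAP content, and their absence from a protocol read without its SAP is not a fault. Whether correlation should give way to bias and limits of agreement is a separate question. Clustering does not decide it.

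**Conclusion.** The concern does not hold. The protocol states neither serial pairs per patient, nor a single pooled coefficient, nor a confidence interval, so it cannot be said to fix any of them badly. The possible effect runs from none (one pair per patient, or an analysis that respects clustering) to coverage of about 65% in the most extreme setting simulated (five pairs per patient, ICC 0.9, clustering ignored). Everything in that range except the 80 patients is assumed, so no size of error can be attributed to this document. What remains is an open detail: the number of pairs per patient and, if there is more than one, how the clustering is handled. That belongs to the SAP. The conclusion would change if the SAP planned repeated pairs and analysed them as independent.

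### The only named outcome is correlation between SpHb and InvHb, which cannot validate the readings for guiding transfusion

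*Protocol*

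**What the plan says.** The Methods paragraph at the front of the protocol words the objective as correlation: "This observational study evaluated the correlation between noninvasive hemoglobin monitoring (SpHb) and invasive hemoglobin measurements (InvHb) in guiding blood transfusions during thoracic surgery". It names one outcome: "The primary outcome will be the degree of correlation between SpHb and InvHb values".

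The purpose it gives for the paired samples is different. Monitoring is continuous, "with simultaneous InvHb samples collected to validate the readings". The Background closes on the phrase "Accuracy of continuous non-invasive hemoglobin monitoring", and the Introduction rests the clinical value on absolute accuracy: "Accurate continuous measures of hemoglobin can help avoid the extremes of over or under transfusion".

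The only design figure is the sample size ("A total of 80 patients aged 18 years or older"). The protocol mentions no bias, limits of agreement, concordance coefficient or acceptable difference, and it does not say which correlation statistic is meant.

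**The concern.** Validation, accuracy and transfusion guidance all turn on how far a reading lies from the reference value in g/dL. Correlation answers another question: whether patients or moments with higher InvHb also tend to have higher SpHb. Three properties make it unsuitable as the main measure here.

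- Adding a constant to every SpHb reading leaves it unchanged.
- Stretching or compressing the SpHb scale by a positive factor leaves it unchanged.
- With device error fixed, it increases with the spread of hemoglobin among those sampled.

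A high coefficient could therefore be taken as validation of a monitor that reads consistently high or flattens true differences. A modest one could reflect nothing more than a narrow hemoglobin range in these patients. In neither case would the primary result state the error of the device.

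**Working it through.** **The plan's own figure.** The sample size of 80 comes with no alpha, power, target correlation, SD or number of pairs per patient, so it cannot be reproduced. For context only: 80 independent pairs give 80% power at two-sided 5% to detect r = tanh((1.960 + 0.842)/√77) = 0.31 against zero. That says nothing about agreement, and the point below does not depend on it.

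**Inputs.** The protocol gives no hemoglobin mean, SD or device error. All such values below are assumptions: InvHb mean 11 g/dL, InvHb SD s, random error SD e, and InvHb taken as the true value.

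**Model.** SpHb = a + b·InvHb + error.

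- Pearson r = b·s / √(b²s² + e²). The offset a does not appear.
- SD of differences = √((b − 1)²s² + e²).
- 95% limits of agreement = mean difference ± 1.96 × SD of differences.
- Concordance coefficient = 2bs² / (s² + b²s² + e² + (mean difference)²).

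**1. Constant offset** (s = 1.5, e = 1.0, b = 1). r = 1.5/√(2.25 + 1) = 0.83 in every row, and the simulated rank correlation is 0.82 in every row.

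| Bias (g/dL) | Pearson r | Limits of agreement (g/dL) | Concordance |
|---|---|---|---|
| 0 | 0.83 | −1.96 to +1.96 | 4.5/5.5 = 0.82 |
| +1 | 0.83 | −0.96 to +2.96 | 4.5/6.5 = 0.69 |
| +2 | 0.83 | +0.04 to +3.96 | 4.5/9.5 = 0.47 |

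With e = 0.7 instead, r is 0.906 at all three biases, while the limits move from −1.37/+1.37 to +0.63/+3.37 g/dL.

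**2. Compressed scale** (s = 1.5, b = 0.5, e = 0.5, correct at 11 g/dL). r = 0.75/√(0.5625 + 0.25) = 0.83 again. The device reads 11 + 0.5 × (8 − 11) = 9.5 at a true 8, and 12.5 at a true 14. Its mean difference is zero and its limits are ±1.96 × √(0.25 × 2.25 + 0.25) = ±1.77 g/dL.

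**3. Spread of hemoglobin** (b = 1, no bias, e = 1.0, so the limits are ±1.96 g/dL throughout).

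| InvHb SD (g/dL) | 1.0 | 1.5 | 2.0 | 2.5 |
|---|---|---|---|---|
| Pearson r | 0.71 | 0.83 | 0.89 | 0.93 |

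The concordance coefficient, 2s²/(2s² + 1), also runs from 0.67 to 0.93 between the two ends of this range.

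**4. Precision of an agreement analysis at n = 80**, assuming one pair per patient and t(79) = 1.99. The 95% CI half-width is t·SD/√80 for the bias and t·SD·√(1/80 + 1.96²/(2·79)) for each limit.

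| SD of differences (g/dL) | Bias (±) | Each limit (±) |
|---|---|---|
| 0.8 | 0.18 | 0.31 |
| 1.0 | 0.22 | 0.38 |
| 1.5 | 0.33 | 0.57 |

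**The case against.** The strongest reply is that the protocol names no coefficient. If a concordance or absolute-agreement coefficient were meant, it would respond to bias, and the choice of statistic is commonly left to an SAP, which is not available here. It is true that no statistic is named. But the plain word, used in both the objective and the outcome, means association, and nothing in the text points elsewhere. A concordance coefficient would also still depend on hemoglobin spread and give no error in g/dL. An SAP that added limits of agreement as a supplement would leave correlation as the primary outcome.

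Second, the study is observational and has no success rule, and agreement could be computed later from the same pairs. This stands as a limit: no pass/fail decision hangs on r, and data collection is not compromised. What suffers is what the primary result can show.

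Third, the Introduction also values reacting to changes in hemoglobin, which a constant offset does not impair. That passage concerns trauma patients, and the outcome correlates values, not changes. A compressed scale would impair detection of change as well.

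Finally, every magnitude is assumed, so the figures show what is possible rather than what is likely in this trial. That is correct. The insensitivity of correlation to offset and scale, however, is algebraic and needs no assumed values.

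**Conclusion.** The concern holds: the primary outcome is wrong as written for the purpose the protocol gives. Reported as planned, the main result would be blind to constant bias and scale error and would depend on the hemoglobin range sampled. Under the illustrative assumptions, one value of r (0.83) is compatible with a device that is unbiased, one that reads 2 g/dL high, and one that halves true differences. A device with unchanged error can score anywhere from 0.71 to 0.93 depending on who is enrolled. This needs correcting before analysis because it is the only outcome the protocol names. Confidence is high for the mismatch itself. The sizes rest on assumed SDs and on ordinary Pearson or rank correlation being meant.

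**What to change.** Amend two sentences in the Methods paragraph.

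- **Objective:** replace correlation with agreement between the two methods.
- **Primary outcome:** *agreement between paired SpHb and InvHb, expressed as the mean difference (SpHb minus InvHb) and 95% limits of agreement in g/dL, each with a 95% confidence interval, allowing for repeated pairs within a patient if more than one is taken, and judged against a maximum acceptable difference set and justified by the investigators before analysis.*

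Also report whether the difference depends on hemoglobin level. For the compressed device above, the ±1.77 g/dL limits contain the +1.5 g/dL error at a true 8, but they do not show that the device overstates low values and understates high ones. Keep correlation as a secondary descriptive measure.

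The cost is a short amendment, a justified acceptable difference, and a different calculation on pairs already planned. The change does not in itself require more patients or samples, but whether 80 is enough depends on the difference chosen, so the investigators should compare it with the half-widths above. If several pairs per patient are taken, the analysis must account for that. With an assumed 3 pairs and a within-patient correlation of differences of 0.5, the design effect is 1 + 2 × 0.5 = 2.0, and ignoring it makes the interval for the bias √2 = 1.41 times too narrow. The one downside is that limits in g/dL may look less favourable than a high r.
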